7.3. Subgroup Analyses

Subgroup analyses will be performed to evaluate differential treatment

on the effects of patients' clinical and sociodemographic characteristics separately for each stratum. Heterogeneity in treatment effects will be explored via subgroup analyses of prespecified prognostic variables in the ITT population. The interactions between the treatment and subgroup variables will be tested by including a multiplicative interaction term (treatment*subgroup variable) in the model. Subgroup analyses will help determine the efficacy of any prespecified subgroup. Statistical significance for each subgroup analysis will be exploratory and conducted at α = 0.05. The subgroup analyses will include:

Alberta Health

- a. Age (<65 years vs. >= 65 years)
- b. Sex (male vs. female),
- c. The side of injury is the same as the dominant hand (no vs. yes)
- d. Race (American Indian/Alaska Native vs. Asian vs. Black/African American vs. Native Hawaiian/Other Pacific Islander vs. White or Caucasian vs. Latino/Hispanic)
- e. Type of injury
 - AO/OTA classification (distal humerus vs. proximal radius and ulna)
 - Distal humerus fracture type (Extraarticular 13A vs. Partial Articular 13B vs.
 Complete Articular 13C)
 - Radius, proximal end segment type 2R1 (Extraarticular fracture 2R1A vs. Partial articular fracture 2R1B vs. Complete articular fracture 2R1C)
 - Ulna, proximal end segment type 2U1 (Extraarticular fracture 2U1A vs. Partial articular fracture 2U1B vs. Complete articular fracture 2U1C)

- f. Concurrent injury (no vs. yes)
- g. Treatment adherence: The number of medications each participant has taken at Week 6 will be used to assess their treatment adherence. The proportion of medication (60%, 70%, and 80%) taken at Week 6 will be used to define three levels of adherence. The subgroup will be adherence vs. no adherence.

Alberta Health

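### Section 7.3 item g treats adherence through Week 6 as a baseline subgroup, at three nested cut-offs; it is a post-randomisation variable, so its subgroup effects and interaction can be biased

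*SAP*

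**What the plan says.** Section 7.3 of the SAP sets one framework for all subgroups. It describes them as "subgroup analyses of prespecified prognostic variables in the ITT population", and the treatment-by-subgroup interaction is "tested by including a multiplicative interaction term (treatment*subgroup variable) in the model". On purpose it says: "Subgroup analyses will help determine the efficacy of any prespecified subgroup". On status: "Statistical significance for each subgroup analysis will be exploratory and conducted at α = 0.05".

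Items a to f are age, sex, whether the injured side is the dominant one, race, injury type and concurrent injury. All are fixed before treatment starts. Item g differs: "The number of medications each participant has taken at Week 6 will be used to assess their treatment adherence". It continues: "The proportion of medication (60%, 70%, and 80%) taken at Week 6 will be used to define three levels of adherence". It ends: "The subgroup will be adherence vs. no adherence". The section gives no separate method for item g, names no lead cut-off, and does not say how results that differ between cut-offs would be read.

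**The concern.** A subgroup comparison is protected by randomisation when the subgroup is fixed before treatment can act on it. Capsules taken by Week 6 do not meet that condition, because tolerability or perceived benefit can change how many are taken. Participants who adhere on ketotifen and those who adhere on placebo may then be differently selected, and the same holds for non-adherers. Splitting on adherence gives up the randomised comparison within each stratum, and hence in the interaction. Using the intention-to-treat population does not restore it.

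At stake is the reading of a neutral or borderline trial. Section 7.3 says the subgroups help to establish efficacy within a subgroup, so a difference among adherers could be reported as a drug effect. Three cut-offs with no lead add room for choice, and the move from three levels to a two-group contrast leaves the actual comparison unclear.

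**Working it through.** The SAP states no figure for this analysis, so there is none to reproduce. The check has three parts: an illustration of bias under no drug effect, a comparison with sampling error, and the error rate over three cut-offs.

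**Inputs from the SAP (Section 4).** Target difference 10°, SD 25°, 127 per arm, 11% dropout. Evaluable per arm: 127 × 0.89 = 113. The SAP gives the SD for the change from baseline to Week 12; I assume that it also serves for the Week 12 outcome.

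**Assumptions not in the SAP.** One dose is compared with placebo. A normally distributed propensity to adhere correlates r with the outcome. Adherence is 85% on placebo and 70% on the dose, with r = 0.3 to 0.5; a smaller gap follows. Positive values favour ketotifen.

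**Formula.** With a proportion p adhering, z its normal cut-point and φ the normal density, mean propensity is φ(z)/p in adherers and -φ(z)/(1 - p) in non-adherers. The spurious difference is the gap in these means between arms, times r, times 25°.

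- Adherers: 0.497 (top 70%) - 0.274 (top 85%) = 0.222 before rounding of the terms.
- Non-adherers: 0.348/0.30 = 1.159 and 0.233/0.15 = 1.554 below the mean; gap 0.395.
- Interaction (adherers minus non-adherers): 0.222 - 0.395 = -0.173.

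| Quantity | r = 0.3 (× 7.5°) | r = 0.5 (× 12.5°) |
|---|---|---|
| Adherers | 1.7° | 2.8° |
| Non-adherers | 3.0° | 4.9° |
| Interaction | -1.3° | -2.2° |

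**Smaller gap.** With 85% v 80%, the adherer means are 0.274 and 0.350, a gap of about 0.076. For r = 0.1 to 0.5 the bias in adherers is 0.076 × 2.5° = 0.2° to 0.076 × 12.5° = 0.95°. If adherence is unrelated to arm, and its link with prognosis is the same in each arm, the bias is zero.

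**Standard errors at 113 per arm (85% v 70%).**

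- Adherers, 96 and 79: 25 × √(1/96 + 1/79) = 3.8°.
- Non-adherers, 17 and 34: 25 × √(1/17 + 1/34) = 7.4°.
- Interaction: √(3.8² + 7.4²) = 8.4°.

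The largest values are 2.8/3.8 = 0.73, 4.9/7.4 = 0.66 and 2.2/8.4 = 0.26 of a standard error. A two-sided 0.05 test then rejects about 7% to 11% of the time in adherers and 5.3% to 5.8% for the interaction.

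**Direction.** It depends on the mechanism. A simulation with no drug effect made adherence depend more strongly on prognosis in the active arm. It assumed a prognostic factor correlated 0.3 with range of motion and 0.5 with the adherence score, and placebo adherence of about 90%, 85% and 80% at the three cut-offs. The spurious effect in adherers was +0.9° to +1.2°, or +1.9° to +2.3° if active-arm adherence was also lower overall. The interaction was then +2.0° to +3.0°, the opposite sign to the table.

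**Three cut-offs.** Three independent tests at 0.05 would give 1 - 0.95³ = 14.3%. These cut-offs are nested; the same simulation set-up, with adherence unaffected by arm and 113 in each of two arms, gives about 10% for at least one false-positive interaction.

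**The case against.** The best defence is that the consequence is limited. Every subgroup test is declared exploratory, the primary analysis follows randomised assignment, and the capsules look identical (Section 3.2), which restrains differences in adherence due to guessed allocation. The SAP reports no difference in adherence or tolerability between arms. The cut-offs overlap heavily and can be read as a sensitivity check on the threshold. All of this stands and bears on the weight of the point. It does not make the contrast a randomised one: identical capsules do not prevent side effects from changing adherence, and the exploratory label concerns strength of evidence rather than bias.

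A reader might infer two stronger things. The first is that item g is certain to give biased effects. The SAP does not support that: bias needs an arm difference in adherence or in its link with prognosis, and neither is documented. The second is that it would tend to yield a false finding that the drug works in those who took it. The main illustration gives the larger spurious benefit in non-adherers, so its interaction points the other way; only a different assumed mechanism reverses it.

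It can also be said that removing item g does not close off such a claim, because the per-protocol population in Section 6 already excludes participants who did not receive the planned dose. That is correct. The per-protocol analysis has a similar selection weakness and does not justify adding a second one.

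**Conclusion.** The point holds as a design weakness in a secondary, exploratory part of the plan. Item g does not belong with subgroups fixed before treatment, and its within-stratum effects and interaction can be biased under no drug effect. The number of cut-offs and the missing lead cut-off add a modest multiplicity problem, about 10% rather than 14.3% under the simulated conditions.

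Size and direction cannot be derived from the SAP. Under the assumptions shown, the bias among adherers runs from about 0.2° to 2.8° against a 10° design difference, and no illustrated value reaches one standard error. The case for change is that the estimate lacks a sound interpretation and the correction is cheap; a large distortion has not been shown. The primary intention-to-treat result is not in question.

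**What to change.** Remove item g from the list of subgroups and interaction tests in Section 7.3. Report adherence descriptively by arm, and state that no claim of efficacy in adherers will be based on it.

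If an adherence-adjusted effect is wanted, prespecify one supplementary causal analysis, done separately for each dose against placebo. Use a single adherence definition, preferably the proportion of doses taken rather than a dichotomy, and state the assumptions, including the exclusion restriction. A complier-average estimate at one cut-off, with randomised arm as the instrument, would not be adequate as it stands: participants below the cut-off still take some drug, which breaks the exclusion restriction, and with two active doses the instrument must be defined for each contrast.

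The cost is a wording change and, if chosen, one extra analysis. The adherence-stratified comparison is lost, and any causal estimate will be less precise and will depend on its assumptions.

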7.4. Handling of missing Data

Based on previous experience with the amount of missing data in the PERK-I trial, it is expected that there will be minimal missing data. Despite the sites' best efforts, some missing data may exist, mainly due to lost-to-follow-up. Efforts will be made to keep all missing data, particularly the primary outcome, to a minimum. Missing data will be assumed to be missing completely at random (MCAR), which means that the probability of missing values in one outcome is unaffected by the observed outcome value or any other variable values. We intend to use the multiple imputation method, which is generally regarded as the least biased since it incorporates the uncertainty of the imputed value. Missing values will be imputed for the primary outcome if the missingness is more than 5% of patients enrolled using the Multivariate Imputation by Chained Equations (MICE) approach. Ten sets of imputed data will be created and analyzed using the model described in Section 7.2. Important baseline data such as sex, age, side of injury is the same as the dominant hand, type of elbow injury, and concurrent injury will be regarded as fixed variables, and site will be included in the multiple imputation model. Type of elbow injury is defined as AO/OTA classification, i.e., distal humerus vs. proximal radius and ulna. Sensitivity analysis will be performed to assess the impact of missing data on the Page **35** of **37**

primary outcome. We expect analyses using data from the multiple imputation methods to

yield conclusions comparable to previous findings in Section 7.2, especially when there is

minimal missing data.

8. Reference List

- 1. Jones V. Conservative management of the post-traumatic stiff elbow: A physiotherapist's perspective. Shoulder Elbow. 2016; 8:134-141
- 3. Siemensma MF, van der Windt AE, van Es EM, Colaris JW, Eygendaal D. Management of the stiff elbow: A literature review. EFORT Open Rev. 2023; 8:351-360

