7.2. Primary, secondary, and safety analyses

The linear regression model will be used to model the mean differences in the range of motion as a function of the intervention received. The unadjusted model will use a univariate linear regression model to assess whether the participants' means of range of motion received Ketotifen Fumarate (2 mg or 5 mg) differed from those who received lactose placebo. A multivariate regression model will be used to adjust for the effect of baseline covariates, i.e., sex, age, side of injury is the same as the dominant hand, type of elbow injury, concurrent injury and site as a random variable. Type of elbow injury is defined as AO/OTA classification, i.e., distal humerus vs. proximal radius and ulna. Table 2 summarizes the statistical analyses.

Table 2: Statistical Analysis of Primary, Secondary, and Safety Endpoints

| Study Endpoint | Statistical Model | Estimate of treatment effects |
|--|--|---|
| | | |
| The mean difference between | Linear regression | The unadjusted mean difference |
| injured and contralateral elbow | This model will be used to obtain the unadjusted mean | and the corresponding 95% |
| flexion-extension at Week 12 | difference between the injured and contralateral elbow | confidence intervals |
| | flexion-extension at Week 12. | |
| | Secondary | |
| The mean difference between injured and contralateral flexion at Week 12 | The data will be analyzed with or without adjusting for specific baseline covariates. The statistical models are described below: a) Linear regression model This model will be used to obtain the unadjusted mean difference between injured and contralateral flexion at Week 12. b) The mixed-effects linear regression model This model will be used to obtain the adjusted mean difference between injured and contralateral flexion at Week 12. b) The mixed effects linear regression model This model will be used to obtain the adjusted mean difference between injured and contralateral flexion at Week 12. The baseline covariates sex, age, side of injury is the same as the dominant hand, type of elbow injury, and concurrent injury will be regarded as fixed variables, and site as a random variable. Type of elbow injury is defined as AO/OTA classification, i.e., distal humerus vs. proximal radius and ulna. | The mean difference and its corresponding 95% confidence intervals for both the unadjusted and adjusted analysis |

Alberta Health Services

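### The SAP's imputation model for Week 12 ROM names neither treatment arm nor earlier ROM; run without arm, it would shrink a true 10° effect to 9.5° at 5% missing and 8.9° at 11%

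*SAP*

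**What the plan says.** All of the following is in SAP Section 7.4 unless noted.

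- Mechanism: "Missing data will be assumed to be missing completely at random (MCAR").
- Reason for multiple imputation: it is "generally regarded as the least biased since it incorporates the uncertainty of the imputed value".
- Trigger: "Missing values will be imputed for the primary outcome if the missingness is more than 5% of patients enrolled", using MICE.
- Analysis: "Ten sets of imputed data will be created and analyzed using the model described in Section 7.2". Section 7.2 models "mean differences in the range of motion as a function of the intervention received", and the primary row of its Table 2 is an unadjusted linear regression, so treatment is the only explanatory term.
- Imputation predictors: "Important baseline data such as sex, age, side of injury is the same as the dominant hand, type of elbow injury, and concurrent injury", "and site will be included in the multiple imputation model". Nothing else is named.
- Role: a sensitivity analysis for missing data is promised without a method, and the imputed results are expected to "yield conclusions comparable to previous findings in Section 7.2".

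Section 5 and Table 1 show that injured-elbow ROM is also measured at Weeks 2, 6, 24 and 52.

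**The concern.** An imputation model should contain every variable in the analysis model that will use the imputed data. Here the main one, treatment arm, is not named. A programmer who follows the list literally will draw each missing Week 12 value from a distribution shared by all three arms, which pulls the arms together.

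The stated rationale also does not fit the stated assumption. Under MCAR, complete cases already give an unbiased comparison, so bias is no reason to impute, and imputing without arm would introduce a bias that was not there. The reason given, that imputation carries its own uncertainty, concerns variance and not bias. Section 7.4 expects most losses to come from loss to follow-up. If such loss is related to early recovery, MCAR fails, and the listed baseline variables cannot correct for it. Week 2 and Week 6 ROM might.

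Finally, the 5% rule reads as though the imputed result replaces the main one, while the closing sentences read as though it is a check on Section 7.2. On the first reading the headline estimate is affected. On the second, a real effect could be made to look fragile.

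**Working it through.** **Inputs.** From SAP Section 4: difference 10°, SD 25°, overall dropout 11%, 381 participants (127 per arm), later 395. From Section 7.4: 5% trigger and ten imputations. Assumptions: the 10° and 25° apply to the Week 12 injured-versus-contralateral endpoint (Section 4 describes them as a change from baseline); 11% stands in for missing Week 12 ROM; missingness is equal across arms.

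**The plan's own figure.** Section 4 gives no power for the recalculation. With 85% power and two-sided 0.05, n = 2 × (1.960 + 1.036)² × (25/10)² = 112.2, so 113 per arm; 113/0.89 = 127 per arm and 381 in total, which matches. Power of 80%, 90% or 95% would give 112, 149 or 184 per arm.

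**Is the trigger reachable?** 0.05 × 395 = 19.75, so 20 missing values are enough. The planned dropout is 0.11 × 395 = 43.45, about 43.

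**Shrinkage.** Let a fraction f be missing in each arm and imputed without arm. Each arm mean becomes (1 − f) × (own mean) + f × (pooled mean). The pooled term cancels in the difference, leaving 10 × (1 − f):

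- f = 5%: 10 × 0.95 = 9.5°
- f = 11%: 10 × 0.89 = 8.9°

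The result is the same whether one dose works or both.

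**Simulation.** 12,000 three-arm trials per setting, MCAR, normal-regression imputation, ten imputations, Rubin's rules, two-sided 0.05. The Monte Carlo standard error of power is about 0.003. Cells show mean estimate and power per comparison.

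| Participants | Missing | Complete cases | MI without arm | MI with arm |
|---|---|---|---|---|
| 381 | 5% | 10.05°, 0.878 | 9.55°, 0.852 | 10.05°, 0.876 |
| 381 | 11% | 10.02°, 0.851 | 8.91°, 0.782 | 10.02°, 0.845 |
| 395 | 5% | 10.01°, 0.884 | 9.51°, 0.862 | 10.01°, 0.882 |
| 395 | 11% | 9.97°, 0.866 | 8.87°, 0.797 | 9.97°, 0.860 |

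The power loss against complete cases is 2 to 3 points at 5% and about 7 points at 11% (0.851 − 0.782 = 0.069; 0.866 − 0.797 = 0.069).

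**Direction.** With one effective dose, 381 participants and 11% missing, the rejection rate for the ineffective dose is 0.030 without arm, against 0.053 for complete cases and 0.055 with arm. The error is conservative.

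**What earlier ROM adds.** With arm in the model, adding Week 6 ROM (381 participants, 11% missing) gives power of 0.851, 0.869 and 0.878 for assumed Week 6–12 correlations of 0.5, 0.7 and 0.9. Week 6 ROM without arm repairs only part of the shrinkage: in a separate simulation of 3,000 trials (assumed correlation about 0.7, half the effect present at Week 6), the estimate was 9.7° at 5% and 9.2° to 9.4° at 11%. When loss was made to depend on Week 6 ROM (assumed correlation 0.7), the estimates were 9.9° with arm and Week 6 ROM, 9.7° for complete cases and 8.6° without arm. Those last sizes depend on how closely loss tracks Week 6 ROM, for which the SAP gives no figure.

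**The case against.** The predictor list is introduced as examples, and nothing excludes arm. The mixed-model rows of Table 2 repeat the same covariate list without naming treatment, although those models must contain it, so the omission may be only a drafting habit. Week 2 ROM is called a baseline value in the ANCOVA rows and could be meant as well. This stands: the defect is an imputation model left open on its key term, and the shrinkage is conditional. But the list is framed as baseline data, which assigned arm is not naturally part of and Week 6 ROM cannot be. The ANCOVA rows also show that the SAP names treatment separately when it chooses to.

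The 8.9° figure needs 11% missing at Week 12. Section 4 gives that rate overall and without a time point, and Section 7.4 expects little missing data. This also stands. Near the trigger the loss is small.

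The imputed analysis may be meant as supportive, which would leave the primary estimate untouched. That is a fair reading, but the 5% rule supports the other one, and the SAP does not settle it.

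Multiple imputation is valid under MCAR, and no passage shows that loss depends on recovery. Under MCAR, leaving out earlier ROM costs only precision. Both points are correct. They make the MAR and earlier-ROM changes improvements, while the bias shown under MCAR comes from omitting arm alone.

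**Conclusion.** The concern holds. Section 7.4 names an imputation model without the variable whose effect the analysis estimates, under an assumption that removes the stated reason for imputing. If arm is in fact left out, a true 10° difference is estimated as 9.5° at 5% missing and 8.9° at 11%. At 11% missing, power per comparison drops by about 7 points: 78% against 85% with 381 participants, or 80% against 86–87% with 395. These figures rest on the Section 4 inputs applying to the primary endpoint, equal missingness across arms, and overall dropout as a proxy for missing Week 12 ROM. The error would understate a real benefit and could not create a false one. It reaches the headline result only if the imputed analysis is primary, which the SAP leaves unclear.

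**What to change.** Revise SAP Section 7.4 as follows:

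1. Replace MCAR with missing at random given the named predictors.
2. Name the full MICE model: treatment arm (or impute separately by arm), injured-elbow flexion-extension arc at Weeks 2 and 6 and at later visits where observed, contralateral arc, the covariates already listed, and site.
3. State whether the imputed or the complete-case Section 7.2 analysis is primary when more than 5% of Week 12 values are missing. The other becomes the sensitivity analysis.

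A delta-adjusted analysis for data missing not at random is an optional addition.

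The cost is a few sentences and a little programming, with no new data. The one drawback is that missing Week 2 or Week 6 values must be imputed in the same chain.
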